Study arm 2: The arm with 100 patients with known or suspected skin cancer will have a scan with the THz skinometer in the clinic prior to their planned skin surgery. They will be scanned on the cancerous area, a control area and a reference standard area (the volar forearm) for a minimum of 3 quality scans. In the event that the reference standard and control area are the same, then the participant will only have a minimum of 2 quality scans. The purpose of the reference standard area scan is to act as a calibration point and so we can compare a between subject variable as well as the within subject variable from the cancer/control area. If a participant has multiple potentially cancerous areas on their body, the team will decide which of these areas to scan for the study. If it occurs that the chosen area is too difficult to scan/doesn't produce a clear enough image then a different cancerous area will be selected. There will be a maximum of 3 scans conducted at each of the cancerous area, control area and reference standard area in order to obtain a meaningful dataset. Later the results of the THz scan will be compared to the formal histology results after the primary (melanoma) or residual (BCC) tumour has been removed.

For patients with multiple skin conditions (i.e. multiple dry skin or cancerous locations on the body), we will select the area that is most practical to scan and can make good contact with the scanner.

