#### 7.2 Baseline data

The following information will be collected as part of baseline data:

- Patient hospital ID number
- Unique study ID assigned to participant
- Demographics including : age, sex, ethnicity, height, weight, BMI
- Provisional clinical diagnosis
- Location of area to be scanned

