For all consenting eligible patients, during the study visit, outcomes will be taken for the affected (area of interest) and unaffected (control) parts of the skin. For each group, a paired t-test will be used to compare the means of outcomes (e.g. skin hydration) for affected and unaffected parts. The corresponding mean difference between affected and unaffected parts and 95% confidence interval (CI) will also be reported. For affected parts, using one way analysis of variance (ANOVA), we will test whether the means for the three groups are equal. Pairwise comparisons using independent t-tests will also be performed, with mean difference and 95% CI reported. We will also compare unaffected parts means for the three groups similarly.

Since this is a feasibility study, we will test all hypotheses at 10% significance level. Also, we will not adjust for multiplicity associated with testing multiple hypotheses. However, for it to be worthwhile conducting a future large study to test utility of THz, clear signals (large differences), estimated using mean differences and 95% CIs, will need to be observed in this feasibility study.

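### The three non-randomised groups are compared on raw affected-area means, so background skin differences between groups can appear as disease differences

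*Protocol*

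**What the plan says.** Protocol section 8 sets out three analyses of the scan outcomes.

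- **Within each group:** "a paired t-test will be used to compare the means of outcomes (e.g. skin hydration) for affected and unaffected parts", with the mean difference and 95% CI.
- **Between groups, affected areas:** "For affected parts, using one way analysis of variance (ANOVA), we will test whether the means for the three groups are equal". Then: "Pairwise comparisons using independent t-tests will also be performed, with mean difference and 95% CI reported".
- **Between groups, control areas:** "We will also compare unaffected parts means for the three groups similarly".

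On the error rate, "we will test all hypotheses at 10% significance level", without multiplicity adjustment. Section 8 adds that large differences, judged by mean differences and 95% CIs, must be seen before a larger study is worthwhile. Section 8.1 gives 80% power for the independent t-test with 50 per group and a standardised difference of 0.5.

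On the scans and covariates:

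- Section 1.4 (study arm 2) says "The purpose of the reference standard area scan is to act as a calibration point", and that it allows a between-subject as well as a within-subject comparison. Both arms schedule this volar-forearm scan.
- The same section provides for overlap: "In the event that the reference standard and control area are the same", the participant has fewer scans.
- Section 7.2 collects "Demographics including : age, sex, ethnicity, height, weight, BMI" and the location to be scanned. Section 8.2.1 uses age, sex, location and provisional diagnosis only to study recruitment.
- Section 8.3 says participants are selected by diagnosis and not randomised. Section 6.1 admits NHS staff to arm 1 only.

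**The concern.** The three groups come from different clinics, one of them includes staff volunteers, and the site scanned is wherever the lesion is or wherever contact is practical. Normal skin may therefore differ between groups in age, sex or body site before any disease is considered. A raw comparison of affected areas cannot separate such a difference from a disease effect.

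The protocol collects what is needed to separate them: a control scan, a forearm reference scan, age, sex and location. None of these enters the affected-area comparison. The forearm scan, whose stated purpose includes between-subject comparison, appears in no analysis in section 8. Because section 8 names the method, this is a stated choice and not a detail left to a statistical analysis plan.

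At stake is the secondary outcome in section 3.4 (a hydration difference between skin types) and the signal for a larger study. Where the forearm also serves as the control area, affected minus control mixes body site with disease as well.

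**Working it through.** **Inputs from the protocol.** 50 per group and d = 0.5 (section 8.1); 10% significance level (section 8). Sidedness is not stated.

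**Assumptions, not in the protocol.** A background shift between two groups of 0.1 to 0.5 SD; a within-person correlation rho between affected and control scans of 0.3 to 0.7; equal SDs at both areas.

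**1. Reproduce the stated power.** The noncentrality is d × sqrt(n/2) = 0.5 × sqrt(25) = 2.5. The normal approximation gives Φ(2.5 − 1.645) = 80.4%; the noncentral t gives 79.9%. One-sided 10% would give 88.6% and two-sided 5% would give 69.7%. The stated 80% is therefore a two-sided 10% test, and it is right.

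**2. Background shift with no disease effect.** The noncentrality is shift × sqrt(25) = 5 × shift (noncentral t, two-sided 10%). The ANOVA column assumes that one group of three is shifted.

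| Assumed shift (SD) | Noncentrality | Pairwise t-test rejects | ANOVA rejects |
|---|---|---|---|
| 0.1 | 0.5 | 14% | 14% |
| 0.2 | 1.0 | 26% | 25% |
| 0.3 | 1.5 | 44% | 44% |
| 0.5 | 2.5 | 80% | 82% |

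The nominal rate is 10%. The estimate moves too: the standard error of a pairwise difference is sqrt(2/50) = 0.2 SD, so a 0.3 SD shift moves the centre of the 95% CI by 1.5 standard errors.

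**3. Strength of the control-area check.** The control-area comparison has the same n and, by assumption, the same SD. Its chance of flagging a 0.3 SD shift is therefore also about 44%. It would miss such a shift more often than not.

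**4. What the alternatives do at d = 0.5 (noncentral t).** For the affected-minus-control difference, the SD is multiplied by sqrt(2(1 − rho)). For ANCOVA on the control scan, it is multiplied by sqrt(1 − rho²).

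| rho (assumed) | Raw t-test | Affected minus control | ANCOVA |
|---|---|---|---|
| 0.3 | 80% | 68% | 83% |
| 0.5 | 80% | 80% | 89% |
| 0.7 | 80% | 94% | 97% |

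**5. What each leaves of a shift common to both areas.** The difference removes it. ANCOVA on one scan leaves about (1 − rho) of it. At rho = 0.5 and a 0.3 SD shift, the noncentrality is 1.5 × (1 − 0.5)/sqrt(1 − 0.25) = 0.87. The test then rejects about 22% of the time (normal approximation): better than 44%, but still above 10%.

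**The case against.** The control scan is not ignored. The paired test in each group is free of between-person differences in age, sex or staff status, and control-area means are compared across groups. These are secondary, exploratory outcomes of a study whose primary outcomes are recruitment counts and willingness. Section 8 asks for large differences before a larger study, so rejection at 10% is not the decision rule. Nothing in the protocol shows that the groups differ in age, site or hydration.

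Most of this stands, and it limits the point. It does not remove it. The paired tests stay within groups, and the control-area result is never combined with the affected-area result. The large-difference rule is read from mean differences and CIs, which a background shift moves directly.

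Three stronger readings are tempting, and the document does not support them:

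- **That confounded differences will be read as disease effects.** They can be, but no imbalance is shown, and the partial checks and the large-difference rule exist.
- **That the plan loses power or misstates it.** The 80% reproduces without adjustment, and any gain depends on a correlation that the protocol does not give.
- **That the forearm scan plays no part at all.** Section 8 does not say how hydration is derived, so calibration could occur before testing. What can be said is that section 8 names no use for it.

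**Conclusion.** The point holds as a weakness of a stated method. The between-group comparison of affected areas is unadjusted in groups that are not randomised, and it leaves out the within-person scan and covariates already collected. Under assumed background shifts of 0.2 to 0.5 SD and no disease effect, a pairwise test rejects 26% to 80% of the time instead of 10%. Those rates describe the test; they do not measure how often a wrong decision to proceed would follow. They rest on the assumed shifts, on equal SDs and on 50 per group.

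Improved precision is a possible secondary benefit, conditional on rho. Since the outcomes are secondary and exploratory, the change is recommended; it is not a condition for the study to be sound.

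**What to change.** Revise the analysis paragraphs of section 8 as follows.

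1. Make the main between-group analysis a comparison of affected-minus-control differences across the three groups, adjusted for age, sex and body-site category, with adjusted pairwise differences and CIs.
2. Add as a second analysis an ANCOVA of affected-area values on group, with control and forearm values, age, sex and body site as covariates. This gives the forearm scan a named use.
3. Keep the raw ANOVA and t-tests as descriptive.
4. Repeat the affected-minus-control analyses, including the paired tests, without participants whose control area was the forearm.

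No new scans, visits or participants are needed. The costs are:

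- A few degrees of freedom are used.
- The difference gains power over the raw test only if rho exceeds 0.5, and falls to 68% at 0.3.
- ANCOVA is more powerful at each correlation shown but does not fully remove a common shift, so it should not stand alone.
- In arm 1, section 1.4 asks for a disease-free forearm only where that can be managed, so this covariate may itself be affected in one group.

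State the assumed rho next to any revised power figure.

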## 1.2 Proposed study

The SINATRA study is pilot study with a primary aim to explore the feasibility of the trial methodology. In addition, secondary objectives of the study will investigate if THz light is able to detect subtle differences in skin hydration and their clinical relevance. Due to the unprecedented sensitivity of THz light to skin hydration, we will also investigate if different skin types have a preferential uptake of certain emollients. This would include dry skin conditions such as eczema, psoriasis and post-operative scars. This will give us information on how to optimise the types of emollients used in future development of new moisturisers and sunscreens. This is already under investigation in a cohort of volunteers with unaffected skin (unpublished pilot study data, University of Warwick). Additionally, as part of the SINATRA study, we will investigate if THz imaging is able to detect subclinical (invisible) skin cancer (residual basal cell carcinoma (BCC)) and enhance the diagnosis of suspected skin cancer (malignant melanoma) in vivo. Skin cancer is known to produce a localised inflammatory reaction and microscopic swelling and so the changes in skin hydration may be able to be objectively measured by THz skinometry.

Terahertz scanner (Investigational Medical Device) and safety:

Terahertz ( $10^{12}$  Hz) pulsed imaging is a new technique with high resolution and has only emerged recently as a potential new clinical tool for medical imaging. It is a safe imaging modality as the light is non-ionising – it has a million times lower energy than an x-ray and thus doesn't have enough energy to cause ionisation. The power levels used in the THz systems in this study are also very low such that there are no lasting effects. In particular, our *in vivo* THz imaging systems have a peak power less than 40mW and average power intensity less than 4  $\mu$ W/cm². Studies by Hough et al [2] have shown that even using peak power 50,000 times higher and an average intensity 30 times higher does not cause any change in gene expression. Therefore, power levels used in our THz in vivo imaging systems are safe and have no known side effects or risks

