## 2. RATIONALE

# 2.1 Aims and hypothesis

The primary aim of SINATRA study is to explore the feasibility of trial methodology

Justification:

The SINATRA trial is an observational study utilising a novel technology thus it is prudent that we collect feasibility data which can inform the development of a definitive trial. We hope that this novel technology, if proven effective, may allow the assessment of emollients and may lead to personalised medicine for the treatment of dry skin conditions. There is also no objective and accepted way to diagnose skin cancer *in vivo* (without biopsy). Current methods are subjective and require training and experience to improve accuracy (clinical examination and dermoscopy). This can result in unnecessary biopsy of benign lesions increasing the risk of patient harm and healthcare costs.

The risk to the patient who is having the scan with the Terahertz (THz) skinometer is negligible. It uses non-ionising radiation, at lower energy that visible light. There is a risk of skin reaction when an emollient is applied. To mitigate this risk, participants will be requested to use emollients they have used previously and they will be requested to bring their own moisturising cream. The scan time is short and painless. The skin area of interest will be placed on the scanner at low pressure. The scanner will be cleaned with standardised clinical cleaning agents between patients. There will be no additional risk compared to standard practice. Patients will be treated in accordance with institutional coronavirus (COVID-19) clinical risk assessments and practice.

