## 3.4 Secondary endpoints/outcomes

**Physiological and clinical outcomes**: The secondary outcome is an objective difference in skin hydration between normal skin, benign skin conditions, skin containing residual basal cell carcinoma and skin containing malignant melanoma. The secondary research end point will be after the comparison of scan data with formal reported histological analysis as part of the standard skin cancer management pathway.

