#### 8.1 Sample size consideration

The target is to recruit at least 50 patients for each of basal cell carcinoma group, malignant melanoma group and benign dry skin conditions group. We anticipate at least 80% of patients who meet eligibility criteria to accept to enrol, that is, recruitment rate is at least 80%. For eligibility rate, we consider the worst case scenario (50% eligibility rate) and low eligibility rate of 20%. We consider three cases of willingness rates (20%, 50% and 80%). Table 1 shows the sample sizes and margins of error (ME), where ME =  $1.96 \times \sqrt{\frac{rate \times (1-rate)}{sample \, size}}$ . The largest number needed to be approached is 1575 patients for each group. As highlighted in the table, we expect a scenario requiring to approach 630 to be closer to the reality. The largest margin of error corresponds to the recruitment rate at 9.9% so that the 95% CI is 70%-90%. We consider this to precise enough for recruitment rate.

For comparing means, power is lowest for independent t-tests. With 50 patients in each group, assuming a moderate effect size (standardised difference of 0.5), the power is 80% at 10% significance level.

Table 1: Sample sizes and margins of errors

Willingness rate	20%	20%	50%*	50%	80%	80%
Eligibility rate	20%	50%	20%*	50%	20%	50%
Recruitment rate	80%	80%	80%*	80%	80%	80%
Willingness: n †	1575	630	630	252	394	158
ME	2.0%	3.1%	3.9%	6.2%	3.9%	6.2%
Eligibility: n ‡	315	126	315	126	315	126
ME	4.4%	8.7%	4.4%	8.7%	4.4%	8.7%
Recruitment: n§	63	63	63	63	63	63
ME	9.9%	9.9%	9.9%	9.9%	9.9%	9.9%

†Corresponds to number approached to be screened; ‡Corresponds to number screened for eligibility; §Corresponds to number eligible; \*Expect reality closer to this scenario.

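### Section 8 compares lesion with control skin and study group with study group, but never splits arm 2 lesions by histology, so its clear signals need not bear on melanoma v benign or residual BCC v none

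*Protocol*

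**What the plan says.** Section 8 plans two kinds of outcome comparison. Within each group, "a paired t-test will be used to compare the means of outcomes (e.g. skin hydration) for affected and unaffected parts". Across groups, for affected skin, "using one way analysis of variance (ANOVA), we will test whether the means for the three groups are equal", followed by pairwise t-tests; unaffected skin is treated in the same way. On significance, "we will test all hypotheses at 10% significance level". The section then says that for a future large study of utility to be worthwhile, "clear signals (large differences), estimated using mean differences and 95% CIs, will need to be observed in this feasibility study". It puts no number on large.

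Histology appears elsewhere:

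- Sections 1.3 and 1.4 say that arm 2 scans will later be compared with the formal histology.
- Section 3.4 defines the secondary outcome as a hydration difference between normal skin, benign conditions, and skin that contains residual BCC or melanoma. It adds: "The secondary research end point will be after the comparison of scan data with formal reported histological analysis".
- Sections 7.3 and 9.1 describe collecting the histology and linking it to the scan data.
- Within section 8, histology appears only as a data source, in 8.4.

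On entry to the groups, section 8.3 selects patients on clinical diagnosis. Section 6.1 admits suspicious pigmented lesions for which a biopsy is planned. BCC patients enter on a histological diagnosis, but whether residual tumour is present at the scan is known only from the later specimen.

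**The concern.** Section 1.2 says the study will investigate whether the scan can "enhance the diagnosis of suspected skin cancer (malignant melanoma) in vivo" and whether it can detect residual BCC. Section 2.1 gives as background to current diagnostic methods: "This can result in unnecessary biopsy of benign lesions increasing the risk of patient harm and healthcare costs". The contrasts that bear on those interests are melanoma v benign among suspicious pigmented lesions, and residual tumour v none among treated or biopsied BCC. Section 8 contains neither.

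Two errors of reading are possible. A clear lesion v control difference could be taken as support for a diagnostic study when benign lesions show the same difference. Conversely, a real melanoma signal could look small because benign lesions sit in the group labelled malignant melanoma. The histology is collected in any case, so either misreading is avoidable.

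**Working it through.** **1. The plan's own figure.** Section 8.1 states: "With 50 patients in each group, assuming a moderate effect size (standardised difference of 0.5), the power is 80% at 10% significance level". With n = 50 per group and d = 0.5, the noncentrality is 0.5 × √(50/2) = 2.5. Two-sided 10% gives Φ(2.5 − 1.645) = Φ(0.855) = 80.4%; the noncentral t gives 79.9%. The figure reproduces. It applies to one study group against another, not to melanoma against benign lesions within the pigmented group.

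**2. A clear paired signal with no separation.** Assume that every pigmented lesion, benign or malignant, differs from its control site by 0.8 SD of the paired difference. The 0.8 is an assumption, since the protocol does not quantify large. With n = 50, the expected t is about 0.8 × √50 = 5.66, against a critical value of 2.01. In 20,000 simulated samples the 95% CI excluded zero in over 99.9%. Because melanoma and benign lesions have the same distribution, the AUC between them is 0.50.

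**3. Dilution.** Now assume that only melanomas differ, by 0.8 SD, and benign lesions not at all. With a share p of melanoma, the group mean is 0.8p and the variance is 1 + p(1 − p) × 0.64. The smallest observed paired difference whose 95% CI excludes zero at n = 50 is 2.01/√50 = 0.28 SD.

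| Assumed melanoma share | Mean | SD | Standardised difference |
|---|---|---|---|
| 20% | 0.16 | 1.05 | 0.15 |
| 30% | 0.24 | 1.07 | 0.23 |
| 50% | 0.40 | 1.08 | 0.37 |

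At shares of 20% and 30% the expected group difference falls below 0.28, although the melanomas themselves differ by 0.8 SD.

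**4. What a mean difference says about individual lesions.** Assuming normal values with equal SD in two classes, AUC = Φ(d/√2), and sensitivity at 90% specificity = Φ(d − 1.2816).

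| d | AUC | Sensitivity at 90% specificity |
|---|---|---|
| 0.5 | 0.64 | 22% |
| 0.8 | 0.71 | 32% |
| 1.0 | 0.76 | 39% |

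These describe the separation of whichever two classes are compared. They are a scale for reading d, not an estimate for this scanner.

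**5. What a histology split could deliver.** The share of melanoma among lesions listed for biopsy is not given. Section 8.2 gives 2–3% of two-week-wait referrals, a different denominator, so a range is shown for 50 pigmented lesions. The AUC half-width uses the Hanley–McNeil formula at a true AUC of 0.80. Power is for d = 0.5 at two-sided 10%.

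| Assumed share | Expected melanomas | 95% half-width of AUC | Power, d = 0.5 |
|---|---|---|---|
| 10% | 5 | ±0.24 | 28% |
| 20% | 10 | ±0.17 | 40% |
| 30% | 15 | ±0.15 | 48% |
| 50% | 25 | ±0.12 | 54% |

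If the referral rate of 2–3% did apply, 1 to 1.5 melanomas would be expected, with a 36% to 22% chance of none (0.98^50 and 0.97^50).

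**The case against.** The strongest reply has five parts.

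- **No go rule is stated.** A reader might infer that a large mean difference triggers a larger study. The text does not support that. It makes large differences necessary for such a study to be worthwhile and does not say they are sufficient. This stands.
- **The secondary outcome is a hydration difference.** The first sentence of section 3.4 says so, and mean differences with CIs measure it directly. This stands in part: the skin types named there are defined by the tumour they contain, which for suspected melanoma and residual BCC only histology can settle, whereas the section 8 groups are not formed that way.
- **The histology comparison is planned.** A reader might infer that the protocol omits it. It does not: sections 1.3, 1.4 and 3.4 state it, and its method may be in an SAP that is not shown. The absence of a method is therefore no finding. What remains is that the comparisons section 8 does fix, and the signal it asks for, rest on unsplit groups.
- **This is a pilot.** The primary aim is feasibility, and utility is left to a later study. That argues against a formal accuracy criterion here, but not against splitting by a result already in hand.
- **Histology subsets may be tiny.** This stands, and it is why an AUC threshold should not decide progression alone.

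**Conclusion.** The point holds in a limited form. As section 8 is written, the malignant melanoma mean can mix melanoma with benign lesions, and the BCC mean can mix sites with and without residual tumour. A clear lesion v control difference can therefore coexist with an AUC of 0.50 for melanoma v benign, and a 0.8 SD melanoma signal can shrink to 0.15–0.37 SD if 20–50% of the lesions are melanoma. These sizes rest on an assumed 0.8 SD, assumed shares and, for the AUC figures, normal values with equal SD; the protocol supplies none of these.

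The claim of no separation is strict for the paired contrast. A difference between study groups does imply some separation of those groups, but pigmented lesions v BCC or v dry skin is not the diagnostic question. For BCC the concern is confined to residual tumour, since the diagnosis itself is histological at entry. The matter affects an exploratory secondary outcome and how its signal is read; it does not touch the feasibility primary outcome.

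**What to change.** In section 8:

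1. Classify arm 2 lesions by the histology result for the outcome analysis.
2. Within suspicious pigmented lesions, compare lesion-minus-control hydration in histologically confirmed melanoma v benign lesions.
3. Within previously excised or biopsied BCC, compare residual tumour present v absent.
4. For each, report the mean difference and, as exploratory, the AUC, both with 95% CIs, alongside the number of histology-positive lesions.
5. Require the statement on clear signals for arm 2 to consider these contrasts as well, and say that lesion v normal-skin differences alone do not support a diagnostic claim.
6. Do not make an AUC threshold the sole progression criterion.

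The cost is protocol or SAP wording and a small analysis on data already collected. The drawback is width: with 5 to 25 melanomas among 50 lesions, an AUC of 0.80 carries a half-width of about ±0.24 to ±0.12, so a clear signal will be harder to claim.
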